Because we are dependent on the physician recording the indication of the laboratory test order to determine appropriateness, he will be prompted to enter an indication if he has failed to do so before validating the order. Physicians in the control group will follow the same procedure, but entering an indication will not result in any preselected tests, instead the physician will be presented with an empty order entry form. In case the control physician has failed to enter a diagnosis, he will be prompted to do so before validating the order.

Physicians will still be able to order laboratory tests through the paper-based form as alternative to the CPOE, especially in situations where there is no computer or internet connection available such as during house-calls.

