### 5.4 Assessment of compliance

Physicians will have the choice to use the paper-based order forms or the CPOE to order laboratory tests. To date, about 30% of physicians use the CPOE for routine ordering of laboratory tests in the three collaborating laboratories, and some physicians have already developed their own personal order sets. We will target physicians who have not previously used order sets but without restrictions concerning proficiency in the use of a CPOE. The rationale for this choice is to include physicians with average 'eHealth literacy' making our results more generalizable. We will measure their compliance throughout the trial period by monitoring the amount of paper-based orders. When a rise in the amount of paper-based orders is noticed for a study physician, he will be contacted by the laboratory or a research assistant to encourage further use of the CPOE.

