### 8.1.1 Patient identification

We will identify eligible patients through the CPOE. All patient data will be included for those patients for which the physicians ordered laboratory tests for one of the 17 study indications. The laboratories will log all the indications for which laboratory tests were ordered, and this will allow them to identify the patients for which we will extract laboratory and patient data. A member of the research team will confirm the eligibility of the patient data for inclusion in the trial.

Patient identification will be done using the pseudonymised national security number of the patient. All patients treated by the family physician for which the online CPOE was used to order laboratory tests will be included in the study without exclusions. Data from patients where the physicians used the paper-based order forms will not be included because the physicians do not document the indication for the laboratory tests in this situation. The pseudonymised national security number of patient can be de-encrypted allowing the study physicians to identify patients enrolled in the study while keeping the research facility blinded to their identity (see section 10 for a full description of the data collection).

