### 8.3.1 Method of implementing the allocation sequence

Randomization will be done using an electronic random numbers generator blinded to the research facility. The research facility will be kept blinded to the allocation, but collaborating laboratories will be able to identify intervention and control physicians. Allocation will be kept blinded to all study physicians until the start of the study. At the start of the study, physicians will be aware of the intervention and their allocation to either the intervention or control arm, however patients and research facility will be kept blinded to this allocation during the study and until after the data analysis.

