#### **Month 12:**

After the intervention period of three months the following data will be provided to the research facility by the collaborating laboratories:

- For each of the 17 study indications, name and value of all tests ordered using the CPOE;
- The total volume of tests for all indications;
- The number of paper-based orders being performed alongside the CPOE and the total volume of tests this comprises.

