These levels are important because we will analyse at the level of the patient or the test (depending on the outcome), but we will recruit physicians and allocate primary care practices. We have calculated our sample size and translated this to the amount of physicians to be recruited and the duration of the study. For these calculations we have made several assumptions based on data from various sources ([De Sutter 2007](#), [Janssens 2014](#)). First, we assume that the average test panel will include 5 study tests. Second, we assume that during the study period each test panel will correspond to one patient (that there will be no multiple test panels per patient). Third, we assume that each physician orders blood tests for 15 patients per week. Fourth, we assume that physicians will use the intervention in 70% of the situations (implying a 30% usage of paper-based orders) based on figures by van Wijk et al ([van Wijk 2001](#)). Fifth, we assume that a primary care practice includes 2.35 physicians, based on the recruitment data from an ongoing cluster randomized trial in primary care ([Heselmans 2013](#)).

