## 9.7 Subject population

We will include all data for test orders ordered through the CPOE. Tests ordered through paper-based order forms will not be included in the analysis as these orders were not subject to the intervention. Of the paper-based orders, a significant amount will be orders made during house calls or situations in which a computerized order entry is not feasible. Additionally, orders through a paper-based order form lack information on the indication for the tests making it impossible to assess whether these tests are (in)appropriate. We will monitor the number of paper-based orders as a measure of implementation success of the CPOE.

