10.2. Analysis methods

10.2.1. Primary outcome analysis

Appropriateness

For the definition of the primary outcome, three numbers are relevant: (a) the number of requested tests which are appropriate, (b) the number of requested tests which are inappropriate and (c) the number of inappropriately not-requested tests. As indicated in section 5b, the latter number is only relevant for diabetes mellitus, chronic kidney disease, rheumatoid arthritis and thyroid disease. Per patient, aggregated over panels if multiple panels are available, the primary outcome is defined by the ratio $(a)/(a+b+c)$. We will refer to this ratio as the proportion of appropriate tests in the remainder.

To assess differences between the allocated groups in the proportion appropriate tests, a logistic generalized estimating equation (GEE) model will be used: of interest are the marginal proportions, not the proportions on patient, physician or PCP level.

The logistic GEE model will include the allocated group and laboratory as factors and PCP as the clustering variable. The effect of the intervention will be expressed as the difference in proportions and will be presented together with its associated 95% confidence interval. The proportion of appropriate tests in the two allocated groups will also be estimated from the GEE model and presented with their 95% confidence intervals.

Appropriateness for the composite of all study tests will be compared between intervention and control groups. Furthermore, an additional analysis will be performed that only includes patients who have no indications in addition to the 17 study indications. This additional analysis will correct for an overestimation of inappropriate tests when more than one indication is selected, including indications not under evaluation. These tests would be considered inappropriate even though they could be appropriate according to one of the other indications not being evaluated.

The analyses will be performed on all patients from all physicians according to their allocated group.

Appropriateness for each study indication separately will be performed as a secondary analysis. In this analysis we will include the number of additional indications for the panel as a factor in the analysis.

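### Paper orders, chosen after allocation by unblinded physicians, are excluded from all analyses: the primary result covers CPOE orders only, and the exclusion conflicts with the test-volume objective

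*Protocol*

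**What the plan says.** Protocol 5.1 keeps paper open to both arms: "Physicians will still be able to order laboratory tests through the paper-based form as alternative to the CPOE". Protocol 8.3.1 says that from the start of the study "physicians will be aware of the intervention and their allocation to either the intervention or control arm", and Protocol 8.10 leaves physicians free to use the intervention or not. Sample size planning in Protocol 9.1 assumes 30% paper use, one figure for both arms.

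Paper orders are then removed. Protocol 9.7 says "Tests ordered through paper-based order forms will not be included in the analysis as these orders were not subject to the intervention", and Protocol 8.1.1 removes the patients' data as well: "Data from patients where the physicians used the paper-based order forms will not be included". A second reason is given: a paper order carries no indication, so its appropriateness cannot be judged. Neither section limits the exclusion to particular outcomes.

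Paper use is tracked. Under Protocol 5.4, "When a rise in the amount of paper-based orders is noticed for a study physician, he will be contacted by the laboratory" or by a research assistant. Under Protocol 8.7 (Month 12) the laboratories must supply "The number of paper-based orders being performed alongside the CPOE and the total volume of tests this comprises". Protocol 8.10 and 9.7 use this only to judge how well the system was implemented. None of the analysis sections (Protocol 9.3 to 9.9, SAP 10.2 and 10.3) uses the paper counts, and the SAP does not mention paper orders. SAP 10.2.1, like Protocol 9.3.2, nevertheless says: "The analyses will be performed on all patients from all physicians according to their allocated group".

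**The concern.** Randomisation makes the practices comparable. It does not make comparable the subset of orders that physicians decide, one at a time and knowing their arm, to place through the CPOE. The intervention changes that screen. Intervention physicians meet preselected tests. Control physicians meet an empty form with the same compulsory indication prompt. Either could encourage paper: the first for a physician who wants a different panel, the second for one who finds the extra entry unrewarding.

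If the share or kind of orders sent to paper differs by arm, the CPOE-only comparison mixes a change in what is ordered with a change in how it is ordered. It could then show an effect that is not there or hide one that is. As planned, a reader could not even see whether paper use differed.

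Test volume has a separate problem. Protocol 3.2.2 sets the population as tests ordered by the physicians whatever the indication, and 3.3.2.2 repeats that all their laboratory tests count. Counting tests needs no indication, so the scoring argument in 9.7 does not apply, yet 9.7 removes paper tests there too.

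**Working it through.** **The plan's own yardstick.** Protocol 9.1.3: 300 physicians × 42 patients = 12,600 patients; × 5 tests = 63,000 tests; ÷ design effect 12.465 = 5,054 independent tests, or 2,527 per arm. For 70.0% against 74.1%:

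- SE = √[(0.70×0.30 + 0.741×0.259)/2,527] = 0.0126
- 0.041/0.0126 = 3.25, and 3.25 − 1.96 = 1.29, which is about 90% power.

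The stated 4.1-point detectable difference therefore reproduces.

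**Effect of the exclusion.** Let P be appropriateness over all orders in an arm, s the paper share and q the appropriateness of the paper orders. The analysis then sees

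P(CPOE) = (P − s × q)/(1 − s).

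Inputs from the protocol: P = 70% (9.1.1) and s = 30% (9.1), used here for control. Assumed, because the documents give no data: the intervention paper share, q, and P = 70% in both arms (no true effect).

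| Intervention s | q (both arms) | Control CPOE | Intervention CPOE | Difference, points |
|---|---|---|---|---|
| 30% | 60% | (70−18)/0.70 = 74.3 | (70−18)/0.70 = 74.3 | 0 |
| 40% | 60% | 74.3 | (70−24)/0.60 = 76.7 | +2.4 |
| 40% | 50% | (70−15)/0.70 = 78.6 | (70−20)/0.60 = 83.3 | +4.8 |
| 20% | 60% | 74.3 | (70−12)/0.80 = 72.5 | −1.8 |
| 20% | 50% | 78.6 | (70−10)/0.80 = 75.0 | −3.6 |
| any | 70% | 70.0 | 70.0 | 0 |

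**Masking.** Take a true effect of 70% to 80%, paper orders 10 points more appropriate than their arm's average, and shares of 40% against 30%. Control is (70 − 0.30×80)/0.70 = 65.7 and intervention is (80 − 0.40×90)/0.60 = 73.3. The analysis shows 7.6 points instead of 10.

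**Equal shares are not proof of no bias.** With 30% paper in both arms and no true effect, let control paper orders be 70% appropriate and intervention paper orders 60%. Control is 70.0 and intervention is (70 − 18)/0.70 = 74.3, a false 4.3 points that a comparison of shares would not reveal.

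**Volume.** Any move to paper lowers the CPOE total. The planned model estimates tests per patient (Protocol 9.3.3.2, SAP 10.2.2), and dropping a paper panel generally drops its patient too. That estimate therefore shifts only if paper panels differ in size from those kept.

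**The case against.** The case for leaving the plan alone has real strength.

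- Paper orders carry no indication and cannot be scored. This stands: they cannot be added to the primary analysis.
- Protocol 3.1 compares CPOE with order sets against CPOE without, and 9.1.1 measures study tests recorded through the CPOE. This also stands: an effect on CPOE orders is a legitimate target. Diluting a 10-point CPOE effect to 0.7 × 10 = 7 points over all orders would answer a different question, not correct an error.
- Protocol 9.7 expects much paper use to come from house calls and similar situations, which may well balance between arms. The 30% is a planning figure for all paper use, not a rate of avoiding the allocated system.
- Intervention physicians can add or remove any test inside the CPOE (5.1), so wanting another panel does not require paper. Eligibility requires agreeing to use the CPOE (7.1), and rising paper use prompts contact (5.4).

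The last two points make differential paper use less likely. They do not show that it was absent. Protocol 5.4 gives no threshold and no comparison by arm.

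On volume, one could note that the comparison line in Protocol 3.2.2 also names the two CPOE versions. That describes the arms; the population there and the outcome in 3.3.2.2 still cover all tests ordered.

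**Conclusion.** The concern holds as a limit on what the primary result covers, a missing comparison by arm, and a conflict over test volume. Inclusion depends on a post-allocation choice by unblinded physicians, so the sentence in SAP 10.2.1 claims more than the analysis covers.

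A reader might infer that the exclusion inflates the intervention effect. The documents do not support that. They give no paper share by arm and no appropriateness for paper orders, and the screens could push paper use either way. The 2.4 to 4.8 points rest on assumed inputs. Reversing the imbalance gives −1.8 to −3.6, and equal shares with equal mix give zero. The figures show only that a plausible imbalance can reach the size of the 4.1-point detectable difference, which is itself a planning figure for 300 physicians.

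A reader might also infer that equal paper shares would clear the result. They would not, because the mix of orders moved to paper could still differ. Nor do the documents show that CPOE-only tests per patient must fall.

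**What to change.** Before the study team is unblinded:

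1. **SAP 10.2.1.** Compare the paper share of orders and of tests by arm, clustered on PCP, using the laboratory counts in Protocol 8.7. Check that counts arrive per practice and include the total number of CPOE orders, which that list does not name.
2. **Primary conclusion.** Word it for orders placed through the CPOE, whatever the comparison shows, and say so beside the all-patients sentence in SAP 10.2.1.
3. **Protocol 9.7.** Limit the paper exclusion to outcomes that need an indication. In SAP 10.2.2, add an analysis of total volume (CPOE plus paper) by arm at physician or PCP level. Paper counts are aggregate and cannot enter the per-patient model.
4. **Any bounding analysis of appropriateness.** Label it as assumption-based and state the assumed share of paper tests that belong to study indications (Protocol Figure 15 uses 1/3). Paper tests for all indications should not be pooled with study-indication CPOE tests.

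The cost is wording and a small extra analysis, mostly on data already due from the laboratories. The downside is that the all-order volume effect may look smaller than the CPOE-only effect.

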## 9.8 Procedure(s) to account for missing or spurious data

Crucial in our study is the reporting of study physicians on both the outcome appropriateness and the outcome missed or delayed diagnosis. We have foreseen two interventions to prevent physicians from failing to document the indications for which he is ordering laboratory test.

1. During the trial period, physicians will not be able to validate a laboratory order without entering one or more indications. Physicians attempting to enter laboratory tests through the

CPOE will be prompted to enter at least one indication before being able to validate the order. This prompt will be deactivated after the intervention period.

2. We foresee a financial incentive for study physicians which will be granted at two intervals: a first part at the end of the data collection for appropriateness, and a second part at the end of the data collection for missed diagnoses through the electronic data collection form. This financial incentive will aid in maximizing data reporting by study physicians and is a strategy for preventing missing data.

With these interventions we believe we will not have to deal with any missing or spurious data and do not foresee any procedures to account for these.

## 9.9 Other statistical considerations.

As mentioned in 9.3.1, restricting our evaluation to the 17 study indications may overestimate the amount of inappropriate tests when multiple indications are documented including an indication not under evaluation. These tests, even though possibly appropriate for the additional indication will be considered inappropriate for the study indication. The subgroup analysis of appropriate tests for those orders containing only study indications will allow us to correct for this overestimation.

## 9.10 Economic evaluation (optional)

**If our trial can show effectiveness, we aim to** perform an economic evaluation of our intervention. The aim of this evaluation is to assess the value-for-money offered by using order sets for appropriate laboratory tests.

We **would** include all direct healthcare costs of performing tests, indirect costs of the intervention and make an assessment of the downstream productivity gains and cost-savings that occur through improved (or more efficient) testing. All costs **would** be assessed from both a healthcare payer and a societal perspective, distinguishing as much as possible between various cost-sharers in the specific Belgian context.

These estimates **would** be compared to various effect measures in order to assess the cost-effectiveness of implementing order sets. A first starting point **would** be to calculate the cost per appropriate laboratory test in both arms of the trial. This **should** provide a direct estimate of the efficiency gains achievable through this intervention.

In addition to these efficiency assessments of improved testing we **would** also investigate the distributional aspects of this measure. We would map patients' socio-economic background and explore:

1. how use of testing is distributed over socio-economic strata in Belgium, and
2. whether use of order sets has an equity impact.

Assessing socio-economic background can be done by contacting patients via surveys, asking physicians to make an assessment of the patients' status (income and overall health) and by assessing whether the physician's practice is located in a relatively deprived area or not.

# 10 DATA HANDLING

## 10.1 Data collection tools and source document identification

Data collection will be performed through the Healthdata.be tool developed and maintained by the Scientific Institute for Public Health (WIV-ISP). This tool allows for secure, encrypted and pseudonymised data transfer from multiple sources into a central data warehouse. Data from a single patient can be collected through this system from more than one source while still ensuring anonymity. The healthdata.be platform uses two software tools to capture and collect data. The HD4DP (health data for data providers) tool captures the data from within the EHR or LIS and allows the data provider to complement the tool with additional data which is not stored in the EHR in a structured format. The source data remains in the database of the data provider and only an excerpt of this source data is transferred to the research facility. Data can be collected continuously or in a one-time fashion depending on the resource. All data is transferred through encrypted channels, using highly secured national ehealth encryption algorithms, to the research facility that can view the

data using the HD4RES (health data for researchers) tool. Figure 17 illustrates the data flows from the data provider to the research facility.

[figure not shown]
[figure not shown]

Figure 17: Data flows using the Healthdata.be project. From <http://www.healthdata.be> (02/05/2017).

Data will be collected from 4 sources: the LIS, the primary care EHRs, directly from the primary care physicians and directly from the patients. Before import into the data warehouse, all data is validated in the 'landing zone' and if required sent back to the data provider for additional information. Each of these data flows will be defined, including a full description of each data element. All these data will be pseudonymised to allow integration of data from a single patient from multiple sources. The identity of the individual patient will be blinded to the research facility at all times. Figure 18 illustrates these data flows. **For a full and detailed description of this process we refer to the deliberation of the Sector Committee for Social Security and Health of the Privacy Commission of May 16, 2017 (CBPL 2017).**

**Figure 18:** Data flows from 4 sources (LIS, primary care EHR, directly from primary care physicians, and directly from patients). Data from these sources is validated (in the landing zone) before it is integrated into the data warehouse. Figure adapted from [www.healthdata.be](http://www.healthdata.be).

Data will be collected and recorded through the LIS of collaborating laboratories or the EHR of study physicians. The collection and processing of data (from patients enrolled in this study) will be limited to those data that are necessary to fulfil the objectives of the study. These data will be collected using secure national ehealth communication tools and processed with the necessary precautions to ensure confidentiality and compliance with applicable data privacy protection laws and regulations. Appropriate technical and organizational measures to protect the data against unauthorized disclosures or access, accidental or unlawful destruction, or accidental loss or alteration will be guaranteed by the WIV-ISP, who will be responsible for data storage. Personnel whose responsibilities require access to personal data agree to keep the data confidential.

Data collection is the responsibility of the research facility under the supervision of the investigator. The investigator will maintain complete and accurate documentation for the study. All source documents will be reviewed by the clinical team to ensure that they are accurate and complete.

As defined in section 1.52 of the ICH Guideline for Good Clinical Practice (ICH E6) source documents may include: original documents, data and records (e.g. hospital records, clinical and office charts, laboratory notes....)

